**5.1.1.d. Predictors and Mediators of Intervention Outcomes.** **1. Self-Efficacy for Diabetes Self-Management** is an eight-item instrument (Cronbach's  $\alpha = 0.83$ ) that measures confidence in performing specific diabetes management tasks with a per item mean of  $6.87 \pm 1.8$ . It has demonstrated correlation with HbA1c levels. **2. Medication Adherence.** We will measure adherence to prescribed diabetes medications using pharmacy refill records from the Corporate Data Warehouse. For each identified medication we will calculate medication possession ratios and refill gaps (See Attachment 7, 8, and 11). We will also capture by self-report the Morisky Medication Adherence scale. This scale allows for identification of patients at highest risk for poor outcomes due to non-adherence as well as recognition of barriers to medication compliance. Responses are scored using a dichotomous scale (yes = 0; no = 1) with higher scores reflecting better medication adherence. The scale has been shown to have good concurrent and predictive validity as well as high internal consistency, indicating good reliability (Cronbach's  $\alpha = 0.83$ ). **3. Depression Symptoms.** The PHQ-8 is an eight-item instrument (Cronbach's  $\alpha = 0.83$ ) that measures depressive symptoms. **4. Exercise.** The Lorig Exercise scale is a six item instrument that measures exercise behavior during a typical week. No Internal reliability reported; test re-test for stretching and strengthening  $r = .56$ ; test-retest for aerobic exercise  $r = .72$ . **5. Diet.** The Diet scale is a ten-item (Cronbach's  $\alpha = 0.73$ ) instrument developed as part of the Diabetes Self-Care Activities survey, a 25- item instrument that measures perceived adherence to diabetes self-care recommendations. **6. Goal-Setting Evaluation Tool for diabetes (GET-D)** is an objective rater scale developed and validated for scoring the quality of goals and action plans articulated by patients in our prior goal-setting

studies (see Attachment 7, 8, and 11). 5. Treatment Fidelity. We will also use a measure, described in § 5.1.F.iii., to objectively rate staff member fidelity to the intervention.

Table 10. Measures	Screen	Baseline	4 M	10 M	Measure	Baseline	4 M	10 M
Screening protocol	X				Intervention Mediators and Moderators			
Primary outcome variables					PHQ-8 Diabetes Self-Care Self-Efficacy	X	X	X

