HbA1c levels	X	X	X	X	Diet/Exercise	X	X	X
Diabetes Distress Scale		X	X	X	Pharmacy refills (database)	X	X	X
Baseline Covariates					Goal-Setting Evaluation Tool	X	X	X
Patient Activation Measure		X	X	X	Attendance in group visits		X	X
Functional Health Literacy measure		X			Post-intervention Implementation variables			
The Spoken Knowledge in Low Literacy in Diabetes (SKILLD) Knowledge Assessment Scale		X			Patient exit interviews (Attachment 7)		X	
Patient Socio-demographics		X			Clinician exit interviews (Attachment 13)			X
Baseline clinical characteristics		X			Summative implementation variables			
PACT and facility characteristics		X			Reach and Adoption measures	X	X	X
Patient knowledge & understanding of DM					Fidelity measures	X	X	X
EQ-5D		X	X	X				
		X	X	X				

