Several variables will be examined as separate mediators of the relationship between intervention group (EPIC versus EUC) and post-intervention outcome variables: 1) patients' perceptions of goal-setting engagement by the designated PACT member (CSQ), 2) objective ratings of goal and action plan quality (GET-D), 3) self-efficacy for diabetes self-management, 4) diabetes self-management adherence, and 5) mediation adherence. For each mediator, we will conduct three separate models to test for mediation between intervention group and each outcome: 1) the first model will regress post-intervention HbA1c levels on treatment group and baseline HbA1c levels, 2) the second model will regress the mediator on treatment group and baseline HbA1c levels, 3) the third model will regress post-intervention HbA1c levels on treatment group, baseline HbA1c levels, and the mediator. Parallel analyses will be conducted to predict change in DDS. We will use bootstrapping methods to calculate the unstandardized estimate of the indirect effects as well as unbiased confidence intervals. Significance will be established if the 95% confidence interval of the indirect effect does not include zero. Bootstrapped analyses will be performed using MPlus Version 6.

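### The exploratory mediation models leave out the mediator's own baseline value, which Table 10 collects for four of the five mediators, so the mediator-to-outcome path is open to avoidable confounding

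*Combined protocol and SAP*

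**What the plan says.** Section 5.6.C.iii sets out three regressions for each mediator. Model 1 is the total effect of treatment on the post-intervention outcome, given its baseline. For model 2, "the second model will regress the mediator on treatment group and baseline HbA1c levels". For model 3, "the third model will regress post-intervention HbA1c levels on treatment group, baseline HbA1c levels, and the mediator". The same set is planned for DDS. An indirect effect counts as significant if its bootstrapped 95% interval excludes zero.

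The mediators are perceived goal-setting engagement (CSQ) and "2) objective ratings of goal and action plan quality (GET-D), 3) self-efficacy for diabetes self-management, 4) diabetes self-management adherence, and 5) mediation adherence". The last item is read here as medication adherence.

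Table 10 (§5.1.I) marks baseline, 4 months and 10 months for "PHQ-8 Diabetes Self-Care Self-Efficacy", "Diet/Exercise", "Goal-Setting Evaluation Tool" and the database row for pharmacy refills. The patient exit interview, which carries the CSQ items, is marked at 4 months only. Sections 5.1.F.iii and 5.1.G.a place it at the last EPIC session.

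Section 5.6.C (Specific Aim 2) also has a general rule: baseline variables that differ between arms at p < 0.25 enter later models as controls or through propensity scores. The mediation paragraph does not refer to it.

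**The concern.** The plan adjusts for where each patient's outcome started but not for where the mediator started. In model 3 the mediator therefore enters as a 4-month level, which mixes change since baseline with lasting differences between patients. A patient who was already confident at enrolment may have both high self-efficacy and better HbA1c at 4 months, with no contribution from EPIC. Randomization does not deal with this, because patients are not randomized to mediator levels.

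The protocol gives reason to take this seriously. Its description of the self-efficacy scale (§5.1.I, predictors and mediators) reports a correlation with HbA1c. Its account of the previous trial (§2.A.iii) attributes benefit to improvement in self-efficacy, which is a statement about change. The survey mediators and the outcome also belong to the same 4-month assessment wave, so time order gives no protection.

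At stake is the mechanism claim. Bias in the mediator-to-outcome path carries into the indirect effect, and bootstrapping the interval does not remove it.

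**Working it through.** **Does a baseline value exist?**

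| Mediator in §5.6.C.iii | Table 10 row | Baseline value |
|---|---|---|
| CSQ | Patient exit interview | No (4 months only) |
| GET-D | Goal-setting tool | Yes |
| Self-efficacy | Shares a row with PHQ-8 | Yes |
| Self-management adherence | Diet/exercise | Yes |
| Medication adherence | Pharmacy refills | Yes |

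So four of the five have one.

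**Size of the bias.** The plan gives no mediation figure to reproduce, so this is an illustration. Write T for treatment, M0 and M1 for the mediator at baseline and 4 months, and Y0 and Y1 for the outcome:

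- M1 = ρ·M0 + a·T + error
- Y1 = 0.5·Y0 + b·M1 + g·M0 − 0.2·T + error (SD 0.75)

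From the documents: 284 patients and 15% attrition, 284 × 0.85 = 241, run as 240. Assumed: M0, Y0 and M1 (within arm) have SD 1; a = 0.40; corr(M0, Y0) = r = −0.2; ρ = 0.3, 0.5 or 0.7; g = −0.2 or 0; b = 0 or −0.2.

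With M0 left out, the mediator coefficient in model 3 estimates b + g·λ, where λ = ρ(1 − r²)/(1 − ρ²r²). For ρ = 0.5, λ = 0.5 × 0.96/0.99 = 0.485. The bias in the indirect effect is a·g·λ, here 0.40 × (−0.2) × 0.485 = −0.039.

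For g = −0.2, with 1,500 simulated trials per row:

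| ρ | λ | a·g·λ | True 0: planned | True 0: with M0 | True −0.08: planned | True −0.08: with M0 |
|---|---|---|---|---|---|---|
| 0.3 | 0.289 | −0.023 | −0.024 | −0.001 | −0.103 | −0.080 |
| 0.5 | 0.485 | −0.039 | −0.039 | 0.000 | −0.119 | −0.080 |
| 0.7 | 0.685 | −0.055 | −0.054 | 0.001 | −0.134 | −0.079 |

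In the true-zero rows the SD of the planned estimate is 0.023, 0.026 and 0.027, so the bias is about 1.0, 1.5 and 2.0 SDs (0.024/0.023, 0.039/0.026, 0.054/0.027). It is proportional to g and to a: halving either halves it, and g = 0 removes it.

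**Precision.** Adding M0 multiplies the standard error of the treatment-to-mediator coefficient by √[(1 − ρ²)/(1 − ρ²r²)] = 0.96, 0.87, 0.72. When g = 0 it multiplies that of the mediator-to-outcome coefficient by the reciprocal: 1.05, 1.15, 1.39. The SD of the indirect effect, planned versus adjusted, at ρ = 0.3, 0.5, 0.7:

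- b = −0.2, g = −0.2: 0.039 v 0.033; 0.043 v 0.033; 0.048 v 0.033 (better)
- b = −0.2, g = 0: 0.034 v 0.033; 0.034 v 0.034; 0.033 v 0.034 (no real change)
- b = 0, g = 0: 0.022 v 0.023; 0.021 v 0.024; 0.021 v 0.029 (worse)

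**Does the p < 0.25 rule cover the gap?** Under randomization a given baseline mediator passes that threshold about 25% of the time, by chance. The confounding arises because M0 predicts both M1 and Y1, and it is present even when the arms are perfectly balanced.

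**The case against.** The models already adjust for the baseline outcome, which may absorb much of what the baseline mediator would explain. Bias remains only if the baseline mediator acts on the 4-month outcome beyond that, and nothing in the documents shows that it does. This stands: the bias is conditional and its size cannot be computed from the plan.

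The p < 0.25 rule might bring in some baseline mediators. That is only partial cover, since it selects on imbalance and not on prediction of the outcome.

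The analysis is labelled exploratory, and other confounders of the mediator-to-outcome path would remain after the change. Both are true. They limit the importance of the point but give no reason to leave out a covariate already collected.

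Four stronger readings are tempting but unsupported:

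- A reader might infer that the omission makes the indirect effect less precise in general. The gain is assured only for the treatment-to-mediator path; the other path can lose as much.
- A reader might infer that the remedy applies to all five mediators. CSQ has no baseline value.
- A reader might infer that every mediator is measured at the same visit as the outcome. The follow-up surveys are by telephone, HbA1c is a separate laboratory draw, refills come from records and CSQ is taken at the last session. Only a shared assessment wave, for the survey mediators, can be claimed.
- A reader might infer that the randomized comparison is compromised. It is not.

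**Conclusion.** The point holds in a limited form. For self-efficacy, diet/exercise self-management, refill adherence and GET-D, the written models omit a baseline covariate that the study collects. This leaves the mediator-to-outcome path, and through it the indirect effect, open to a known and avoidable source of confounding.

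On the assumed inputs, a true indirect effect of zero would be estimated at about −0.02 to −0.05, and a true −0.08 at about −0.10 to −0.13. These figures rest on the assumed correlations and on a direct effect of −0.2. With no such effect there is no bias, and with the opposite sign the bias would run the other way. They show a plausible scale and do not predict this trial's result.

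The primary analyses (H2 and H3) do not use these models and are unaffected. This is a cheap improvement.

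**What to change.** In §5.6.C.iii, state that for self-efficacy, diet/exercise self-management, pharmacy-refill adherence and GET-D, the mediator's baseline value is a pre-specified covariate in models 2 and 3, for both HbA1c and DDS, whether or not the arms differ on it at baseline.

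Treat CSQ separately. It has no baseline value and is described as collected at the last EPIC session, so as written the treatment-to-mediator path has no control-arm data. Table 5 (§5.5.A) speaks of patients' perceptions of goal-setting engagement in both arms. The sections need to be reconciled before a CSQ mediation model is kept.

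Optionally, as a check on time order, repeat the models with the 4-month mediator and the 10-month outcome, both already scheduled.

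The cost is a few sentences of analysis-plan wording and one extra covariate per model, with no new data. The drawback is a possibly larger standard error for the mediator-to-outcome coefficient, so the change should be justified by reduced bias and not by precision.

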5.6.C.ii. H3 Analyses (Maintenance) Analyses for examination of maintenance of treatment effects will be similar to those for immediate treatment effects post-intervention. We will again employ ANCOVA to examine treatment differences in outcomes at the post-maintenance (10-month) assessment. We will conduct two models: one with HbA1c at 10-months as the outcome and one with DDS at 10-months as the outcome. Models will include treatment group (EPIC versus EUC) as a predictor and respective HbA1c and DDS post-intervention scores and any demographic, clinical, or patient-centered variables that differed between the study arms at baseline as covariates. We will calculate treatment effect sizes at the 10-month assessment.

5.6.C.iii. Exploratory Analyses (Implementation and Effectiveness) We will use a mixed-model approach to conduct separate repeated-measures analyses for HbA1c and DDS simultaneously using all three assessment time points. We will employ growth curve analyses using SAS Proc Mixed to examine overall group differences in improvements or decrements in outcomes over the year, maximize participant data, and account for dependency between patients within a given group session, PACT, and site. Conditional models will contain fixed terms for the intercept, treatment (EPIC or EUC), assessment time period, treatment by time period interaction, and previously identified variables that differ between treatment groups. Modeled random effects will include between-patient variation in baseline scores (i.e., the intercept where baseline assessments are scored 0) and variation in the slopes for time. With three assessments, the focus will initially be on linear patterns of change, although we will evaluate the relative fit of a quadratic pattern of change using the likelihood ratio test. These analyses will allow us to examine the immediate impact of treatment at post-intervention as well as retention, improvement, or decay in outcomes post-maintenance period. The treatment effect will assess differences between the two groups at baseline, the fixed effect of time will measure the average change over time in the outcome (collapsing across the two treatment groups), and the time by treatment interaction will indicate whether change over time (in slopes) differs between EPIC and EUC.

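### The exploratory mediation models do not require the mediator to precede the outcome, so for three of the five mediators a significant indirect effect cannot show direction

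*Combined protocol and SAP*

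**What the plan says.** Section 5.6.C.iii sits under the heading "5.6.C.iii. Exploratory Analyses (Implementation and Effectiveness" and lists five candidate mediators: the CSQ, GET-D ratings of goals and action plans, self-efficacy, diabetes self-management adherence, and medication adherence. They are examined one at a time: "Several variables will be examined as separate mediators of the relationship between intervention group (EPIC versus EUC) and post-intervention outcome variables".

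Three regressions are planned per mediator. The first is the outcome on arm and baseline HbA1c. In the second, "the second model will regress the mediator on treatment group and baseline HbA1c levels". In the third, "the third model will regress post-intervention HbA1c levels on treatment group, baseline HbA1c levels, and the mediator". Parallel models are planned for DDS. The decision rule is: "Significance will be established if the 95% confidence interval of the indirect effect does not include zero". No mediator time point, baseline mediator term or 10-month outcome appears.

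On timing, the documents give:

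- **Table 10 (5.1.I):** the rows "PHQ-8 Diabetes Self-Care Self-Efficacy" and "Goal-Setting Evaluation Tool", as well as diet/exercise and pharmacy refills, are scheduled at baseline, 4 months and 10 months. HbA1c and DDS are measured at the same three points.
- **5.1.H.ii:** follow-up questionnaires are taken by telephone, 4 to 6 months after randomisation. HbA1c is a separate draw within 2 weeks of the target time, or a clinical value from the collection window.
- **5.1.G.a:** the CSQ is completed after the last group session.
- **5.1.I.d (printed 5.1.1.d):** refill adherence is computed from pharmacy records, with no interval defined.

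**The concern.** A product-of-coefficients test reads an association between mediator and outcome, given arm, as an effect of mediator on outcome. That reading needs the mediator to come first. Here, for self-efficacy, self-management adherence (which I take to be the diet and exercise scales) and GET-D, the 10-month reading follows the 4-month outcome and the baseline reading precedes treatment. Only the reading from the outcome's own window is left. A patient whose glucose or distress has already improved may report more confidence because of it. The case is plainest for DDS, which is collected by the same telephone follow-up as self-efficacy. For HbA1c, the draw may come before or after the call.

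The bootstrap deals with sampling error, not with direction. At stake is a statement about how EPIC works, which the plan would declare from an interval that excludes zero.

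**Working it through.** **1. Size of the analysis set (5.6.A).** Per arm, 2(1.960 + 0.842)²/0.40² = 98.1, so 99 (plan: 100). The design effect is 1 + 11 × 0.0183 = 1.2013, giving 120. Then 120/0.85 = 141.2, so 142 per arm and 284 in total, as stated. With 15% attrition, 284 × 0.85 = 241. I used 240 to keep the arms equal.

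**2. A world with no mediation.** The outcome has SD 1, T is arm, and the arm effect at 4 months is 0.40 SD (the plan's d). Not in the documents, and so assumed: a baseline to 4-month outcome correlation of 0.5, a 4 to 10-month correlation of 0.7, a mediator-outcome correlation λ of 0.2 to 0.5, and no clustering. The mediator is generated only from the outcome:

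- Y1 = 0.5·Y0 − 0.40·T + e, with var(e) = 0.75
- M1 = −λ·Y1 + √(1−λ²)·u
- Y2 = 0.7·Y1 + noise

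The true indirect effect is zero.

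**3. What the planned regressions estimate.** The arm-to-mediator path is a = 0.40λ. Given arm and Y0, var(M1) = 1 − 0.25λ², so the mediator-to-outcome path is b = −0.75λ/(1 − 0.25λ²). The standard error of a is about √[(1 − 0.25λ²)/60].

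| λ | a | b | a×b | share of 0.40 | a/SE |
|---|---|---|---|---|---|
| 0.2 | 0.080 | −0.152 | −0.0121 | 3% | 0.62 |
| 0.3 | 0.120 | −0.230 | −0.0276 | 7% | 0.94 |
| 0.5 | 0.200 | −0.400 | −0.0800 | 20% | 1.60 |

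The simulated means of a×b were −0.0124, −0.0285 and −0.0777. The product is not zero in expectation, so a larger sample would not remove it.

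**4. How often mediation is falsely declared** (2,000 simulated trials per setting, Monte Carlo 95% interval for a×b):

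| Model | λ=0.2 | λ=0.3 | λ=0.5 |
|---|---|---|---|
| Planned, same window | 7% | 16% | 35% |
| Planned plus baseline mediator | 7% | 16% | 35% |
| 10-month outcome, no 4-month outcome term | 3% | 10% | 34% |
| 10-month outcome, adjusted for 4-month outcome and baseline mediator | 0.4% | 0.7% | 1.2% |

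A percentile bootstrap (300 trials, 500 resamples) gave 13% and 33% for the planned model at λ = 0.3 and 0.5. With no arm effect on the outcome, the planned model gave 3% to 6%. Two other set-ups, with assumed reverse effects of 0.2, 0.3 and 0.4 SD per SD, gave 10%, 22%, 28% and 8%, 13%, 21%. The lagged model stayed near 1% or below in both.

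Rows 2 and 3 matter for the fix. Neither the baseline mediator nor a later outcome alone restores direction; the 4-month outcome must be in the lagged model.

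**5. What the lagged model gives up.** All path values here are assumed.

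- *Mediation real and complete by 4 months* (arm to mediator 0.4 to 0.5 SD, mediator to outcome 0.3 to 0.5): the planned model detected it in 84% to 97% of trials, the lagged model in 4% to 6%. A separate run gave 91% to 98% against about 5%.
- *A further later effect of 0.1:* lagged detection was 33% to 45%.
- *A later effect of 0.2 to 0.3* (arm to mediator 0.4): lagged detection was 89% to 95%.
- *A shared cause of mediator and outcome, one assumed setting:* the lagged model falsely declared mediation in 44% of trials, the planned model in 33%.

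**The case against.** The strongest reply is that the plan asks what mediates the post-intervention effect, and a lagged model asks something else. By adjusting for the 4-month outcome it removes whatever mediation was complete by then, the period in which EPIC is mainly delivered. Step 5 bears this out, so the lagged model cannot take the place of the planned one.

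It is also fair that the analysis is labelled exploratory, that the false-positive rates rest on assumed correlations, and that GET-D is an objective rating by blinded staff (Table 5), so the self-report explanation does not carry over to it unchanged. Even so, GET-D shares the window and its direction is not established.

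A reader might infer that all five mediators are measured at the same visit as the outcome. The documents do not support that. Section 5.6.C.iii gives no mediator timing, and the shared window is an inference from Table 10. The CSQ follows the last group session, although sessions may run to 6 months, so it is not guaranteed to come first either. Refill adherence covers an unstated interval, and HbA1c is a separate draw. A reader might also infer that the trial's main conclusions are at risk. They are not: H2 and H3 do not use these models.

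**Conclusion.** The point holds for self-efficacy, self-management adherence and GET-D. The planned models do not place the mediator before the outcome, and the decision rule can declare an indirect effect when the influence runs the other way. Under assumed reverse effects or correlations of 0.2 to 0.5 and an arm effect of 0.40 SD, this happened in about 7% to 35% of simulated trials. In the set-up worked through above, 3% to 20% of the arm effect was wrongly credited to the mediator. The documents give no figure for the reverse effect, so these are ranges, not predictions. For the CSQ and refill adherence the point is not clear.

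This is a low-cost improvement to an exploratory analysis. It does not show that a mediation finding from this trial would be false, only that the planned model could not tell.

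**What to change.** Change the SAP wording in 5.6.C.iii as follows.

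1. State which reading of each mediator is used, and the interval for refill adherence.
2. Keep the planned same-window model and add the baseline mediator to the mediator and outcome regressions. Report its indirect effect as an association without established direction.
3. Add, not substitute, a lagged model. Regress the 4-month mediator on arm and the baseline mediator and outcome. Regress 10-month HbA1c (or DDS) on arm, the 4-month mediator, the 4-month outcome and the same baselines. Bootstrap the product. The H3 model already adjusts the 10-month outcome for the post-intervention score, so this is a small extension of it.
4. Claim support for temporal order only where the lagged model agrees.
5. State the limits: the lagged model tests later change only, has almost no power for mediation completed by 4 months, and does not remove shared confounding. A null lagged result does not refute mediation.

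The measures for the three affected mediators and both outcomes are already scheduled. The cost is one more model per mediator and outcome, with somewhat fewer patients contributing 10-month data.
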